#### Table 1: Continuous baseline variables to be reported

Variable	Unit of	Precision	CRF where data are recorded
	measurement	(decimal	
		places)	
BMI z-score	-	2	Derived from height and weight data
(participants			contained in Baseline CRF. See Section
registered at			17.4.2.5.1 below for derivation.
paediatric centres)			
BMI	m/kg²	1	Derived from height and weight data
(participants			contained in Baseline CRF. See Section
registered at centres			17.4.2.5.1 below for derivation.
treating adults)			
Time from	days	0	Baseline – Section 3: date of report
Pseudomonas			confirming P.aeruginosa isolation.
isolation to treatment			Treatment CRFs, Section 1: date started
initiation*			treatment / date started.
%predicted FEV1	litres	2	Raw FEV1 data contained in Baseline
(participants aged 5 or			CRF. See Section 17.4.2.3.1 below for
older only)			derivation.
%predicted FVC	litres	2	Raw FVC data contained in Baseline
(participants aged 5 or			CRF. See Section 17.4.2.3.1 below for
older only)			derivation.
%predicted FVC 25-75	litres	2	Raw FVC data contained in Baseline
(participants aged 5 or			CRF. See Section 17.4.2.3.1 below for
older only)			derivation.
O 2 Saturation	%	2	Baseline

\*Calculated as the number of days from the date of report confirming *P.aeruginosa* isolation to the date of treatment commencement.

Variable	Categories	CRF where data are recorded
Age-group (a)	Infants and toddlers (28 days – 23 mths)	Derived from continuous value obtained from Baseline CRF
	Children (2-11 yrs)	
	Adolescents (12-17 yrs)	
	Adult: 18-64 yrs	
	Elderly adult: ≥ 65 yrs	
Gender	Male	Baseline
	Female	
Pseudomonas	Naïve	Baseline
status	Free	
Other	Candida	Microbiology (see Section
microorganisms	MRSA	17.4.2.12.1 below for derivation)
detected	Burkholderia cepacia	
	Aspergillus	
	Other organisms	
Genotype	F508/F508	Baseline
	F508/other	
	F508/unknown	
	other/other	
	Diagnosis not based on genetics	
Pulmonary	Yes	Baseline (see Section 17.4.2.6.1
Exacerbation	No	below for derivation)

#### Table 2: Categorical baseline variables to be reported

(a) EudraCT defined age-groups – these are different to the categorisations/definitions used in the rest of the study

#### **17.3 Compliance with treatment**

Arm A: Serum creatinine concentration prior to first tobramycin dose administration and tobramycin serum trough concentration prior to second dose administration and after one week of treatment will be presented. Reasons for any tests not being done will be summarised if provided.

The number of doses of ceftazidime that patients receive varies as some sites offer three times daily dosing and others twice daily dosing. The number of doses of tobramycin also varies as some sites offer once daily dosing, some offer twice daily dosing and some offer three times daily dosing. For this reason and because it is stated in the protocol that patients should receive at least 10 days of treatment, compliance for these drugs will be presented in terms of the number of days on treatment rather than the number of doses received.

Arm B: The protocol defines treatment duration for Ciprofloxacin as 3 months. This may be interpreted by clinicians as 3x28 days or 3x30 days. For the purposes of calculating compliance, the Chief Investigator has defined this as 3x28 days. This means that each patient should receive 168 doses (based on them receiving two doses daily). The number of doses patients actually received is recorded in the treatment diary. The compliance rate is calculated by dividing number of doses actually received by the number of doses that a patient should have received (168).

All: To calculate the number of Colistin doses a patient should have received, the number of days between treatment commencement date and the three month visit date will be calculated and multiplied by 2 (based on them receiving two doses daily). The number of doses patients actually received is recorded in the treatment diary. The compliance rate is calculated by dividing number of doses actually received by the number of doses that a patient should have received.

All compliance data will be summarised by total (n), mean, SD, median, interquartile range, range, minimum and maximum regardless of whether the data are normal or skewed. No formal statistical testing will be undertaken.

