#### 8.2 Treatments studied

Full descriptions of the treatments and dose guidelines can be found in Section 6.1 of the protocol. In brief:

Arm A: 14 days\* intravenous (IV) antibiotics as follows:

- Ceftazidime in 3 divided doses three-times daily (tds) (or alternatively a once/twice daily continuous infusion)
- Tobramycin once daily (od) (maximum 660mg /day) (or alternatively a two/three-times daily regimen)

\*Recommended treatment duration should be 14 days, minimum treatment duration should be no less than 10 days

Arm B: 3 months\*\* oral ciprofloxacin twice daily (bd).

Both treatment arms will also receive 3 months\*\* of nebulised colistin in conjunction with the randomised treatments.

\*\*Three months is defined as 12 weeks

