#### 8.9 Schedule of assessments

Table 3 in Section 7 of the protocol outlines the schedule of assessments.

Note that for the purpose of this trial, a 'month' is defined as 28 days. Visits should have occurred as follows:

	Scheduled study visit	Time after treatment start
T 3	3 months	12 weeks
$T_6$	6 months	24 weeks
T 9	9 months	36 weeks
T 12	12 months	48 weeks
T 15	15 months	60 weeks
T 18	18 months	72 weeks
T 21	21 months	84 weeks
T 24	24 months	96 weeks

Due to large numbers of visits occurring outside of appropriate visit windows and not consistently being captured on scheduled or unscheduled visit CRFs; where outcomes refer to specific time points, data will be included based on dates of assessments rather than CRF names. For an assessment to be associated with a particular time-point it must have occurred within 1 week either side of the expected visit date, apart from  $T_{15}$  which may be minus 1 week or plus 2 weeks of the expected visit date.

Not all patients were followed up after  $T_{15}$ .  $T_{18}$ ,  $T_{21}$  and  $T_{24}$  were proposed in the protocol up to and including version 7. Patients randomised after 1st January 2016 were required to complete up to and including  $T_{15}$  only.

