#### 17.4.1.1 Derivation

The CRF: *Microbiology Form* captures information on samples taken at all attended visits (scheduled and unscheduled). The variable MBDSTD gives the date the sample was taken, and the variable MBOC6C indicates that *P. aeruginosa* was cultured if it is selected (MBOC6C = "Pseudomonas aeruginosa").

Success: If there is no record of *P. aeruginosa* on a patient's microbiology CRF between 3 months and 15 months after treatment commencement.

Failure: If there is at least one record of *P. aeruginosa* on a patient's microbiology CRF between 3 months and 15 months after treatment commencement.

Any positive samp	Outcome		
<3 months	3-15 months	>15 months	
×	×	×	Success
×	×	✓	Success
✓	×	×	Success
✓	×	✓	Success
×	$\checkmark$	×	Fail
×	$\checkmark$	✓	Fail
✓	$\checkmark$	×	Fail
✓	$\checkmark$	$\checkmark$	Fail

To determine if a patient has eradicated *P. Aeruginosa* at 3 months, they must have a sample within 28 days either side of the expected 3 month visit date (treatment commencement date + 84 days) which is at least 2 days after the last date of any anti-pseudomonal treatment.

To determine if a patient has remained *P. Aeruginosa* free at 15 months, they must have either a positive sample within the primary outcome window (3-15 months) or they must have a sample within 28 days either side of the expected 15 month visit date (treatment commencement date + 420 days). Patients who have not regrown *P. Aeruginosa* and do not have a sample within the 15 month window (defined above) will not be included in the primary analysis. If a patient is withdrawn before 15 months of follow-up is completed, they will only be included in the primary outcome analysis if they have failed. If there is no evidence that they have failed prior to being withdrawn they will not be included in the primary analysis.

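### Expected colistin doses are counted to the three-month visit date instead of over the 12-week course the SAP defines, so the compliance rate depends partly on when the visit took place (minor)

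*SAP*

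**What the plan says.** SAP section 8.2 states that both arms receive three months "of nebulised colistin in conjunction with the randomised treatments". The footnote attached to that duration, shared with ciprofloxacin, reads "Three months is defined as 12 weeks".

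Section 17.3 then sets two different rules for expected doses:

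- **Ciprofloxacin:** the section notes that clinicians might read three months as 3x28 or 3x30 days. It settles on 3x28 and fixes the expected number at 168 doses.
- **Colistin (both arms):** "the number of days between treatment commencement date and the three month visit date will be calculated and multiplied by 2", on the basis of two doses daily.

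For the numerator, the SAP says "The number of doses patients actually received is recorded in the treatment diary". It does not say whether doses after the three-month visit count.

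Section 8.9 explains that assessments are assigned to time points by date: "Due to large numbers of visits occurring outside of appropriate visit windows". The general window is one week either side of the expected date.

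**The concern.** By the SAP's own definitions, colistin and ciprofloxacin are both twice-daily courses of 12 weeks, yet one section gives them different denominators without a reason. The colistin denominator is a visit date, which says nothing about how many doses were due. If colistin stops at 12 weeks and the visit is late, the drug-free days before the visit count as missed doses. If the visit is early, the denominator is shorter than the course.

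The rule also has no fallback for a patient without a three-month visit. Section 14.2 provides for early discontinuation and withdrawal, so such patients are foreseeable. They would drop out of the table even if they have diary data, and they may include some of the least adherent.

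Colistin is the treatment common to both arms, and this rate is the SAP's only summary of how well it was taken. Section 17.3 reports the mean, SD, median, quartiles and extremes, so distortions from visit timing would show in the table.

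**Working it through.** **Inputs**

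- Course length: 12 weeks = 84 days (section 8.2).
- Frequency: two doses daily (section 17.3).
- Denominator as written: 2 x D, where D is the number of days from treatment start to the three-month visit (section 17.3).
- General assessment window: 84 ± 7, so day 77 to day 91 (section 8.9).
- Window for the three-month culture: 84 ± 28, so day 56 to day 112 (section 17.4.1.1). It is used here only to illustrate a wider departure.

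**The plan's own figure.** 3 x 28 x 2 = 168 doses for ciprofloxacin. This reproduces exactly. Applied to colistin, the 12-week definition gives the same number: 84 x 2 = 168.

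**Which visit date is meant.** Where the SAP means day 84 it says so. Section 17.4.1.1 requires that "they must have a sample within 28 days either side of the expected 3 month visit date" and defines that date as commencement plus 84 days. Section 17.3 leaves out the word expected and has the interval calculated for each patient, which would be pointless if the answer were always 84. The natural reading is the actual visit date.

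**Score of a patient who takes all 168 doses and stops at day 84**

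- All diary doses counted: 168 / (2D).
- Doses counted only up to the visit: min(168, 2D) / (2D).

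| Visit day D | Expected doses 2D | All diary doses counted | Doses counted to visit only |
|---|---|---|---|
| 56 | 112 | 150.0% | 100.0% |
| 77 | 154 | 109.1% | 100.0% |
| 84 | 168 | 100.0% | 100.0% |
| 91 | 182 | 92.3% | 92.3% |
| 112 | 224 | 75.0% | 75.0% |

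For late visits both ways of counting give the same shortfall. For early visits a rate above 100% appears only when doses after the visit are counted.

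**Check of the alternative denominator.** With a fixed 168 and no cut in the numerator, a patient who continues colistin to a late visit would score 182/168 = 108.3% at day 91 and 224/168 = 133.3% at day 112. Fixing the denominator alone is therefore not enough. Numerator and denominator must cover the same 84 days.

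**The case against.** The strongest defence is that the rule may be deliberate. Section 17.3 recognises that clinicians may read three months in different ways. If patients stayed on colistin until they were seen, dividing by twice the days to the visit gives a full complier 100% at any visit date, and a fixed 168 would not. That is a coherent intention, but the SAP does not state it, and it conflicts with the 12-week definition that section 8.2 attaches to colistin. So the defence affects which way the sections are reconciled and does not remove the need to do it.

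A reader might infer that a fully compliant patient can score anywhere from 75% to 150%. The documents do not support that range:

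- It borrows the ±28-day window for the culture sample, which does not limit the visit date in section 17.3. That section sets no limit. The general ±1-week window gives 92.3% to 109.1%, and section 8.9 gives no distribution for the visits outside it.
- The 150% end needs doses taken after a day-56 visit to be counted, which the SAP neither says nor excludes.
- The borrowed window also requires the sample to be at least two days after the last anti-pseudomonal treatment. If that covers colistin, a patient who took the full 84 days could not have a qualifying sample on day 56.

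The 75% end is firmer: it needs only a day-112 visit and colistin stopped at 12 weeks.

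A reader might also infer a spurious difference between the arms. That would need visit timing to differ by arm, and nothing in the SAP indicates that it does.

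Finally, the consequence is limited. Section 17.3 rules out formal testing of compliance. The non-compliance deviation in section 15 uses days of IV treatment and ciprofloxacin doses. No analysis set in section 17.1 is defined by colistin compliance. All of this stands.

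**Conclusion.** The inconsistency between sections 8.2 and 17.3 is real, and section 17.3, followed as written, gives misleading rates for visits away from day 84. For a patient who takes all 168 doses and stops at 12 weeks, the rate is 92% at day 91 and 75% at day 112. It exceeds 100% for an early visit (109% at day 77) only if later diary doses are counted. A patient with no three-month visit has no rate.

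This rests on two assumptions: that the three-month visit date is the actual date, and that colistin stops at 12 weeks as section 8.2 defines. If colistin continued to the visit, the late-visit shortfall disappears. How many patients are affected cannot be told from the SAP, which says only that many visits were outside their windows.

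The point is minor. It concerns one descriptive table and leaves the primary analysis and the non-compliance deviation untouched.

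**What to change.** Reconcile sections 8.2 and 17.3, with the sponsor stating which colistin period was intended.

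- **If the 12-week definition in section 8.2 stands:** set expected colistin doses in section 17.3 at 168 and count diary doses over the same 84 days from commencement, whatever the visit date. Patients without a three-month visit then have a denominator.
- **If colistin was meant to run until the visit:** state that in section 17.3, count diary doses only up to the visit, amend section 8.2 to agree, and say how patients without a three-month visit are handled.

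Either way, numerator and denominator then cover the same period.

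The cost is a short wording change and one table, using diary data already collected. The small downside of the first option is that doses must be cut at day 84, which requires diary entries that can be placed in time. For Arm A patients treated partly in hospital and partly at home, section 8.3 already requires two diaries to be combined.

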## 17.4 Analysis of outcomes

#### 17.4.1 Primary outcome

The primary outcome is successful eradication of *P. aeruginosa* three months after the start of treatment, remaining infection free through to 15 months after the start of treatment (Yes/No).

#### 17.4.1.1 Derivation

The CRF: *Microbiology Form* captures information on samples taken at all attended visits (scheduled and unscheduled). The variable MBDSTD gives the date the sample was taken, and the variable MBOC6C indicates that *P. aeruginosa* was cultured if it is selected (MBOC6C = "Pseudomonas aeruginosa").

Success: If there is no record of *P. aeruginosa* on a patient's microbiology CRF between 3 months and 15 months after treatment commencement.

Failure: If there is at least one record of *P. aeruginosa* on a patient's microbiology CRF between 3 months and 15 months after treatment commencement.

Any positive samp	Outcome		
<3 months	3-15 months	>15 months	
×	×	×	Success
×	×	✓	Success
✓	×	×	Success
✓	×	✓	Success
×	$\checkmark$	×	Fail
×	$\checkmark$	✓	Fail
✓	$\checkmark$	×	Fail
✓	$\checkmark$	$\checkmark$	Fail

To determine if a patient has eradicated *P. Aeruginosa* at 3 months, they must have a sample within 28 days either side of the expected 3 month visit date (treatment commencement date + 84 days) which is at least 2 days after the last date of any anti-pseudomonal treatment.

To determine if a patient has remained *P. Aeruginosa* free at 15 months, they must have either a positive sample within the primary outcome window (3-15 months) or they must have a sample within 28 days either side of the expected 15 month visit date (treatment commencement date + 420 days). Patients who have not regrown *P. Aeruginosa* and do not have a sample within the 15 month window (defined above) will not be included in the primary analysis. If a patient is withdrawn before 15 months of follow-up is completed, they will only be included in the primary outcome analysis if they have failed. If there is no evidence that they have failed prior to being withdrawn they will not be included in the primary analysis.

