## 1 Change Control

Protocol version	Updated SAP version no.	Section number changed	Description of change	Date changed
9.0	2.0	15.0	Clarification that the protocol deviation relating to treatment non-compliance should be based on a cut-off of 120 doses (out of 168 doses) for the Ciprofloxacin arm to be consistent with the cut-off of 10 out of 14 days of treatment for the IV arm. This was a recommendation from the blind review.	23/08/18
9.0	2.0	17.2	Age removed from the baseline characteristics table as a continuous variable and presented only as a categorical variable. %predicted FEF 25-75 and O 2 saturation added to the baseline characteristics table. All continuous baseline characteristics to be presented as mean and standard deviations. These were recommendations from the blind review. Also, CFQ quality of life measures removed from baseline characteristics table as it is not possible to combine different domains into a total score. Minor amendments to the presentation of genotyping data consistent with the way data has been captured.	23/08/18
9.0	2.0	17.4.1.1	
 
Clarification added that
 
For a sample to be classed as the T3 sample for the primary outcome analysis it must be taken within 4 weeks either side of the expected T3 visit date and the patient must have stopped treatment at least 2 days before this
 
For a sample to be classed as the T15 sample for the primary outcome analysis it must be taken within 4 weeks either side of the expected T15 visit date
 
Por a sample to be classed as the T15 sample for the primary outcome analysis it must be taken within 4 weeks either side of the expected T15 visit date
 
Patients who do not have a sample within the T3 window defined above will not be included in the analysis of eradication at 3 months.
 
Patients who do not have a sample within the T15 window and have not previously grown P. Aeruginosa within the primary outcome analysis.
 
These were recommendations from the blind review.
 
	23/08/18
9.0	2.0	17.4.2.3 .2	Results to be presented at specific time points rather than as change from baseline. This was a recommendation from blind review. Also wording added to say that co-efficients from the model will be presented to be consistent with the report shell document and wording added to clarify that a treatment group*time interaction term would be added to the model.	23/08/18

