## 9 Listing of Outcomes

#### 9.1 Primary outcome

Successful eradication of *P.aeruginosa infection* three months after allocated treatment has started, and remaining infection free through to 15 months after the start of allocated treatment.

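### A patient can be a primary Success without the off-treatment 3-month sample that the SAP itself requires to determine eradication, and no sensitivity analysis tests this

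*SAP*

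**What the plan says.** SAP section 9.1 defines the primary outcome as eradication "three months after allocated treatment has started, and remaining infection free through to 15 months after the start of allocated treatment". Section 17.4.1 repeats both parts as a single yes/no endpoint.

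Section 17.4.1.1 then sets out four things:

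- **Classification.** Success is the absence, and Failure the presence, of any recorded *P. aeruginosa* "on a patient's microbiology CRF between 3 months and 15 months after treatment commencement". The table below it sorts positives into before 3 months, 3 to 15 months, and after 15 months. Only the middle column changes the result.
- **T3 sample.** To determine eradication at 3 months, "they must have a sample within 28 days either side of the expected 3 month visit date (treatment commencement date + 84 days", and it must be a sample "which is at least 2 days after the last date of any anti-pseudomonal treatment".
- **T15 sample.** To determine freedom from infection at 15 months, a patient needs either a positive in the 3-to-15-month period or a dated sample: "they must have a sample within 28 days either side of the expected 15 month visit date (treatment commencement date + 420 days". No off-treatment condition is attached.
- **Exclusions.** Patients without regrowth who lack a T15-window sample, or who withdraw early without having failed, leave the primary analysis. No exclusion is stated for a missing or on-treatment T3 sample.

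Section 17.4.1.2 reports positives at the 3-month visit as a separate summary. The Change Control entry for 17.4.1.1 presents the window and the 2-day condition as what qualifies a sample as T3 in the primary analysis, but then gives this consequence of lacking one: "Patients who do not have a sample within the T3 window defined above will not be included in the analysis of eradication at 3 months".

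**The concern.** The 2-day condition presumably exists because a negative culture taken under anti-pseudomonal treatment does not show eradication. Having set that standard, the derivation does not apply it to the endpoint that needs it. Success then combines two kinds of patient: those shown to be clear at 3 months who stayed clear, and those whose 3-month status was never validly established but who had no positive on record later.

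The null hypothesis in section 7 is about patients who eradicate at three months and then remain free. If the first part is not checked, the relative risk in section 17.4.1.2 describes a somewhat different endpoint. Two programmers could also read 17.4.1.1 differently and produce different primary results.

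**Working it through.** The SAP gives no event rate or sample size (section 10 refers to the protocol), so there is no figure to reproduce. The check applies the written rule to dated sample histories.

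**Inputs.** A month is 28 days (section 8.9), so 3 months is day 84 and 15 months is day 420. Both windows are ±28 days (17.4.1.1). Colistin runs 12 weeks in both arms (section 8.2). Section 17.3 notes that three months of ciprofloxacin may be read as 3×28 = 84 or 3×30 = 90 days.

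**Windows.**
- T3: 84 − 28 = 56 to 84 + 28 = 112, which is 57 days.
- T15: 420 − 28 = 392 to 420 + 28 = 448.

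**When a valid T3 sample is possible**, for a patient who completes treatment:
- Last treatment on day 84: earliest valid day 84 + 2 = 86, leaving 112 − 86 + 1 = 27 of 57 days.
- Last treatment on day 90: earliest valid day 92, leaving 112 − 92 + 1 = 21 of 57 days.

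So with treatment to day 84, a sample on the expected visit date itself does not meet the 2-day condition. Lacking a valid T3 sample is therefore not a remote possibility, although this says nothing about how often it happened.

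**The rule as written.** Fail if any positive falls on days 84 to 420; otherwise Success if any sample falls on days 392 to 448; otherwise excluded. For comparison, the second column requires valid off-treatment samples at both T3 and T15, and counts a positive in either of those samples as Fail.

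| History | As written | Valid T3 and T15 required |
|---|---|---|
| No T3 sample; negative day 420 | Success | Not determinable |
| Negative day 84 on treatment; negative day 420 | Success | Not determinable |
| Off-treatment positive day 80; negative day 420 | Success | Fail |
| Off-treatment negative day 90; on-treatment negative day 420 | Success | Not determinable |
| Off-treatment negatives on days 90 and 420 | Success | Success |

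Rows 1 and 2 are the main point. In row 3 the day-80 culture lies in the T3 window and meets the 2-day condition, so it is a valid positive T3 sample. The table nevertheless puts it in the before-3-months column, and the patient is a Success. Row 4 shows the separate T15 gap.

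**Longest unsampled stretch the rule allows.** From day 84 to a first sample in the T15 window: 392 − 84 = 308 days to 448 − 84 = 364 days.

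**Sensitivity analyses.** Sections 19.1.1 to 19.1.3 concern patients without a T15-window sample. Section 19.1.4 concerns centre. None varies the handling of a missing or on-treatment T3 sample, or of an on-treatment T15 negative.

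**The case against.** The best defence is that the T3 requirement sits inside the primary outcome derivation, is worded as mandatory, and is linked to the primary analysis in Change Control. On that reading a valid T3 negative is already required and only the wording is loose. This stands in part: it makes the matter a conflict between two readings rather than a settled omission. It does not remove the problem, because the Success rule, the table and the list of exclusions all follow the other reading. A change log is not operative text, so the point rests on 17.4.1.1 set against 9.1 and 17.4.1; the log only shows that the intent is not clear there either.

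It is also fair that visits are scheduled at T6, T9 and T12 (section 8.9) and that samples from all attended visits are captured. A persisting infection would have several chances to be recorded. The 308-to-364-day gap is permitted, not typical.

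A reader might infer that the rule favours one arm, because oral patients take ciprofloxacin up to T3 while IV patients stop after about two weeks. The SAP does not support this. The condition counts from the last date of any anti-pseudomonal treatment, and colistin is planned for 12 weeks in both arms.

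A reader might also infer that trial treatment carries over into the T15 culture. Planned treatment ends on day 84, 308 days before that window opens. The T15 question is only whether a later, unrelated antibiotic course suppressed the culture. Excluding on-treatment T15 negatives from the primary analysis while keeping on-treatment positives would make inclusion depend on the culture result and on antibiotic use after randomisation. The objection to doing that is sound.

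**Conclusion.** The point holds as a conflict in the primary endpoint derivation. Followed literally, 17.4.1.1 awards Success without valid evidence of eradication at 3 months, although the stated outcome and the T3 condition in the same section call for it. The T15 gap is also real but lesser: the off-treatment condition applies to T3 only.

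The size is unknown. The share of Successes misclassified on the T3 part would be the proportion lacking a valid T3 sample multiplied by the proportion of those who were in fact still infected at 3 months. The SAP gives neither, so any percentage-point figure would be invented. The direction is equally open, and no imbalance between arms is shown. The classification results assume that 3 and 15 months mean days 84 and 420, as the SAP defines them. The counts of valid T3 days also assume that treatment is completed to day 84 or day 90; earlier stopping makes earlier samples valid.

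**What to change.** 1. **Section 17.4.1.1.** State whether a valid off-treatment T3 negative is part of Success, and make the rule, the table and the exclusions agree. Say how patients without a valid T3 sample are classified, and how a positive inside the T3 window but before day 84 is scored.
2. **Section 19.1.** Add a sensitivity analysis of all patients with a valid off-treatment T3 sample, whatever happened later. Failure is a positive at that sample or any positive to T15. Success is negative at T3, no later positive, and a T15-window sample as 17.4.1.1 already requires. Patients meeting neither definition remain not evaluable. Report by arm how many primary Successes lacked a valid T3 sample.
3. **T15.** Where antibiotic dates are recorded, report by arm how many Successes rest only on an on-treatment T15 negative. Treat them as not evaluable in a sensitivity analysis only, leaving the primary analysis set unchanged.

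The cost is some wording, counts by arm, and one or two extra runs on a smaller and less precise subset. Item 3 depends on dates of non-trial antibiotics about a year after treatment, and the SAP names no form or variable for these. If they were not collected, say so as a limitation.

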#### 19.1.3 Results of blind review

Derivation and analysis as in Section 17.4.1.1 and Section 17.4.1.2 but all patients that have been followed up for more than 15 months but not had a sample within the 15 month window will be included. These patients will be classified as success or failure based on the next sample that was taken following the 15 month window.

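### Read literally, the primary-outcome rule scores a patient as a Success when the qualifying 15-month sample is positive on days 421 to 448

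*SAP*

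**What the plan says.** Section 8.9 fixes the time unit: "for the purpose of this trial, a 'month' is defined as 28 days". Three months is therefore day 84 and fifteen months is day 420, and section 17.4.1.1 itself gives both day counts.

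Section 17.4.1.1 then contains two rules.

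- **Classification.** Failure requires at least one *P. aeruginosa* record "on a patient's microbiology CRF between 3 months and 15 months after treatment commencement", and Success requires none. The accompanying table has separate columns for positives before 3 months, from 3 to 15 months, and after 15 months. A patient positive only before 3 months, only after 15 months, or only in both of these periods, is a Success.
- **Qualifying samples.** For eradication at 3 months, "they must have a sample within 28 days either side of the expected 3 month visit date", and the sample must be at least 2 days after the last anti-pseudomonal treatment. For 15-month status, the patient needs either "a positive sample within the primary outcome window (3-15 months" or a T15 sample: "they must have a sample within 28 days either side of the expected 15 month visit date (treatment commencement date + 420 days". A patient with neither is left out of the primary analysis.

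The 3-15 month outcome window and the 15-month sample window are named separately in the same paragraph. Nothing says that a positive sample inside a visit window but outside days 84 to 420 counts as a 3-15 month positive.

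**The concern.** The classification interval stops at day 420, while the sample meant to establish 15-month status may be taken up to day 448. Between those days a T15 sample admits the patient to the primary analysis, but its result has no influence: negative gives Success and positive also gives Success. Such a positive is direct evidence that the patient was not infection free at the defining visit.

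The same clinical finding would be scored differently according to whether the visit fell on day 420 or day 421. Two competent programmers could also produce different primary results, depending on whether they followed the table or its presumed intent. Late visits are a practical matter here: section 8.9 reports that many visits fell outside their windows. The trial is open label, so this choice should not remain open when allocation is released.

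**Working it through.** **Inputs from the SAP.** A month is 28 days (section 8.9). Both sample windows are ±28 days, the classification interval is 3 to 15 months, and the table is as described above (all section 17.4.1.1).

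**Reproducing the stated day counts.** 3 × 28 = 84 and 15 × 28 = 420. Both agree with section 17.4.1.1, and with the 12 and 60 weeks in section 8.9 (12 × 7 = 84; 60 × 7 = 420).

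**Windows.**

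- T15: 420 − 28 = 392 to 420 + 28 = 448, which is 448 − 392 + 1 = 57 days. Days 421 to 448 are 28 of these (28/57 = 49%).
- T3: 84 − 28 = 56 to 84 + 28 = 112, also 57 days. Days 56 to 83 are 28 of these.

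**Applying the rules literally to test patients.** Each has a single positive and is otherwise negative at every visit.

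| Only positive sample | In primary analysis? | Scored as written | Scored if qualifying-sample positives count |
|---|---|---|---|
| T15, day 415 | Yes | Failure | Failure |
| T15, day 420 | Yes | Failure | Failure |
| T15, day 430 | Yes | Success | Failure |
| T3, day 84 | Yes | Failure | Failure |
| T3, day 70 (off treatment) | Yes, with a T15-window sample | Success | Failure |

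**How often the T3 case can arise.** Section 8.2 schedules nebulised colistin for 12 weeks (84 days) in both arms, and a valid T3 sample must be at least 2 days off all anti-pseudomonal treatment. A patient who completes the course cannot have a valid T3 sample before about day 86. Valid samples on days 56 to 83 therefore come mainly from patients who stopped all such treatment early. To be misclassified, they must also have no positive on days 84 to 420.

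**Illustrative size at T15.** The SAP gives no failure rate and no distribution of visit dates, so the following are assumptions:

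- cumulative failure p of 30 to 60%;
- a constant hazard h at each of five scheduled samples (T3, T6, T9, T12, T15);
- a share s of 30 to 70% of T15 samples taken after day 420.

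Then h = 1 − (1 − p)^(1/5), the proportion first positive at T15 is (1 − h)^4 × h, and the proportion misclassified is s times that.

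| p | h | First positive at T15 | s = 30% | s = 50% | s = 70% |
|---|---|---|---|---|---|
| 30% | 0.069 | 5.2% | 1.6% | 2.6% | 3.6% |
| 45% | 0.113 | 7.0% | 2.1% | 3.5% | 4.9% |
| 60% | 0.167 | 8.0% | 2.4% | 4.0% | 5.6% |

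**Effect on the relative risk.** Take true failure of 30% and 45% in the two arms and s = 50% in both. Observed failure becomes 30 − 2.6 = 27.4% and 45 − 3.5 = 41.5%. The failure ratio moves from 30/45 = 0.667 to 27.4/41.5 = 0.660, slightly away from 1. The success ratio moves from 70/55 = 1.273 to 72.6/58.5 = 1.241, slightly towards 1. Section 17.4.1.2 does not say which ratio will be reported.

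**The case against.** The strongest reply is that the text can be read so that the problem disappears. The ±28-day sample is introduced as the one that determines whether the patient is still clear at 15 months, and a positive sample cannot show that. The change control table (section 1) also describes a sample in that window as the T15 sample for the primary analysis. On that reading it belongs in the 3-15 month column. This is probably what the authors meant. It is stated nowhere, however, and the table and the two separately named windows point the other way, so the gap stands.

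Four stronger inferences are tempting, and the SAP does not support them.

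- *That the rule dilutes the treatment contrast, or biases it by arm.* In the example above the success and failure ratios move in opposite directions relative to 1, both slightly. Nothing in the SAP shows that visit timing differs by arm.
- *That the T3 gap exposes every patient first positive at T3.* The 12-week colistin course and the 2-day off-treatment rule confine it mainly to early stoppers.
- *That section 8.9 sets a conflicting T15 window.* Its rule ("which may be minus 1 week or plus 2 weeks of the expected visit date") is general, and the ±28-day rule is specific to the primary outcome and governs there. A cross-reference is enough.
- *That a positive on day 440 is a Success while one on day 460 is a Failure in the same analysis.* A patient with no earlier regrowth and no T15-window sample is excluded from the primary analysis. Only the sensitivity analysis in section 19.1.3 classifies that patient, "based on the next sample that was taken following the 15 month window". Its treatment of late positives suggests that the authors did not intend positives inside the window to be successes.

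**Conclusion.** The point holds for T15. As written, a patient with no positive on days 84 to 420 and a positive qualifying sample on days 421 to 448 is included in the primary analysis and scored a Success, against the evident purpose of that sample. The affected zone is 28 of the 57 window days. At T3 the same gap exists on days 56 to 83, mainly for patients who stopped all anti-pseudomonal treatment early.

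The number of patients involved, and the size and direction of any effect on the relative risk, cannot be derived from the SAP. The 1.6 to 5.6% range rests entirely on the assumed failure rate, the constant hazard per sample and the assumed share of late T15 samples. It shows that the matter may not be negligible and is not an estimate for this trial. Because the rule decides who is a failure on the primary endpoint, it should be settled before allocation is released.

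**What to change.** Reword section 17.4.1.1 along these lines:

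- **Failure:** any positive culture from day 84 through day 420; or a positive sample that qualifies as the T3 sample (days 56 to 112, at least 2 days off treatment); or any positive sample in the T15 window (days 392 to 448). If there are several T15-window samples, any positive one counts.
- **Success:** no such positive, and at least one T15-window sample, all of them negative.
- **No T3-window sample:** the patient is assessed from day 84.

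Realign the table so that positives on qualifying T3 samples and on T15-window samples sit in the 3-15 month column. Keep the strict day 84 to 420 cut as a sensitivity analysis. Add a note that the T15 window in section 8.9 does not govern the primary outcome.

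The cost is SAP wording and one programming rule, with no new data. The small downside is that positives up to 28 days after the nominal 15 months count as failures, although the outcome is worded as running to 15 months. The strict-cut sensitivity analysis will show whether that matters.
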